Appendix [20.2.2](#) shows example SAS code for MI analysis.

10.4 Exploratory Analyses for the Primary Efficacy Endpoint

Adjusted Chi-square Test

Since all subjects from the same household will be assigned to the same treatment group, an exploratory analysis will be conducted on the primary efficacy endpoint in mITT based on an adjusted Chi-square test to account for clustering of the data (Jung et al., 2001). The proportion of subjects with clinical resolution in the study eye will be compared between SHP640 ophthalmic suspension and placebo with missing data imputed with post baseline LOCF for the determination of clinical resolution in the study eye at Visit 3 (Day 5). Adjusted Chi-square test statistics and corresponding p value will be presented.

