6.2.2 Allocation of Subjects to Treatment

This is a double-masked, placebo-controlled study. The actual treatment given to individual subjects is determined by a randomization schedule.

Subject numbers are assigned to all subjects as they consent to take part in the study. Within each site (numbered uniquely within a protocol), the subject number is assigned to subjects according to the sequence of presentation for study participation.

The randomization number represents a unique number corresponding to investigational product allocated to the subject, once eligibility has been determined. Individual subject treatment is automatically assigned by the IRT.

Randomization will be stratified by age to maintain the randomization ratio among subjects <6 years, 6 to <18 years, and subjects ≥ 18 years.

Subjects will be randomly assigned to receive SHP640, PVP-I 0.6%, or placebo based on a 3:1:3 ratio (SHP640:PVP-I:placebo) within the randomization strata.

Multiple subjects from the same household will be eligible to participate in the study. Subjects from the same household will be assigned to the same treatment group to which the first enrolled subject in the household was randomized in order to prevent treatment administration errors or potential treatment unmasking. Dynamic balanced allocation ([Pocock and Simon, 1975](#)) will be used in this study to maintain the randomization ratio within each stratum. The randomization will be done centrally.

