10.2 Primary Efficacy Endpoint and Analysis

The primary efficacy endpoint is clinical resolution status (defined as absence [ie, a score of 0] of bulbar conjunctival injection and ocular conjunctival discharge) in the study eye at Visit 3 (Day 5) between SHP640 and placebo.

The null hypothesis to be tested is that there is no difference in proportion of subjects with clinical resolution in the study eye between SHP640 ophthalmic suspension and placebo with the alternative of the non-zero difference in the proportion with clinical resolution between them. The proportion of subjects with clinical resolution will be compared between SHP640 and placebo groups using two-sided Fisher's Exact test at two-sided 4.99% level of significance. Missing data will be imputed based on post baseline LOCF for the determination of clinical resolution in the study eye at Visit 3 (Day 5). The primary basis of inference for this comparison will be based on the analysis conducted in mITT. Frequency and percent of subjects who reached/did not reach clinical resolution in the study eye at Visit 3 (Day 5) will be reported by treatment group along with the two-sided Fisher's Exact test p value for comparison between SHP640 and placebo. The two-sided 95% CI for response rate (exact CI for binominal proportion) in each treatment group as well as the estimated difference in response rates and corresponding two-sided 95% asymptotic CI for the difference will also be reported.

Example SAS code for conducting Fisher's exact test and generating the CIs is in Appendix [20.2.1](#).

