10.3 Sensitivity Analyses for the Primary Efficacy Endpoint

ITT Population Analysis

A sensitivity analysis will be conducted by repeating the primary analysis using the ITT Population. Frequency and percent of subjects who reached/did not reach clinical resolution in the study eye at Visit 3 (Day 5) will be reported by treatment group along with the two-sided Fisher's Exact test p value for comparison between SHP640 and placebo. The two-sided 95% CI for response rate (exact CI for binominal proportion) in each treatment group as well as the estimated difference in response rates and corresponding two-sided 95% asymptotic CI for the difference will also be reported.

Missing Data Imputation

Method 1: Modified Worst Observation Carry Forward (WOCF)

The between-treatment group comparison (SHP640 versus placebo) for the primary efficacy endpoint will be performed using Fisher's Exact test on the mITT data set. Missing data will be imputed based on post baseline WOCF for the determination of clinical resolution in the study eye at Visit 3 (Day 5). For clinical resolution status, not reaching clinical resolution is considered worse than reaching clinical resolution. If a subject has no post-baseline efficacy assessment up to Visit 3 (Day 5), then his/her baseline efficacy assessment will be carried forward as the Visit 3 (Day 5) assessment.

Frequency and percent of subjects who reached/did not reach clinical resolution in the study eye at Visit 3 (Day 5) in the imputed data set will be reported by treatment group along with the two-sided Fisher's Exact test p value for comparison between SHP640 and placebo. The two-sided 95% CI for response rate (exact CI for binominal proportion) in each treatment group as well as the estimated difference in response rates and corresponding two-sided 95% asymptotic CI for the difference will also be reported.

Method 2: Multiple imputations

Multiple imputation (MI) methods will utilize the SAS procedures PROC MI and PROC

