10.5 Key Secondary Efficacy Endpoints and Analysis

The key secondary efficacy endpoint of this study is bacterial eradication status (defined as absence of all bacterial species present at or above pathological threshold at baseline) in the study eye at Visit 3 (Day 5) between SHP640 and placebo.

The null hypothesis to be tested is that there is no difference in proportion of subjects reaching bacterial eradication in the study eye at Visit 3 (Day 5) between SHP640 and placebo with the alternative hypothesis of non-zero difference in the proportion of responders between the two treatment groups.

In order to maintain the study-wide Type I error at 5% (two sided alpha of 0.0001 at IA and two sided alpha of 0.0499 at final analyses), the primary and key secondary hypotheses will be tested sequentially using two-sided Fisher's exact test with the primary efficacy endpoint being tested first and the key secondary efficacy endpoint being tested second. The hypothesis test for the key secondary efficacy endpoint will not be performed unless the hypothesis test for the primary efficacy endpoint is statistically significant.

Missing data will be imputed based on the post baseline LOCF for the determination of bacterial eradication status in the study eye at Visit 3 (Day 5). The primary basis of inference for the key secondary comparison will be based on the analysis conducted in mITT. Frequency and percent

of responders in the study eye at Visit 3 (Day 5) will be reported by treatment group along with the two-sided Fisher's Exact test p value for comparison between the two treatment groups. The two-sided 95% CI for response rate (exact CI for binominal proportion) in each treatment group as well as the estimated difference in response rates and corresponding two-sided 95% asymptotic CI for the difference will also be reported.

Sensitivity and exploratory analyses will also be conducted on key secondary efficacy endpoint using the same methods as described in Section 10.3 and 10.4 (i.e. modified WOCF imputation and multiple imputation as sensitivity analyses; adjusted Chi-square test and analysis based on CRF visits as exploratory analyses) except for the ITT population sensitivity analysis, which will not be conducted for bacterial eradication key secondary endpoint.

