20.2 Example SAS Code

20.2.1 Example SAS Code for Fisher's Exact Test and the CIs

Example SAS code for conducting Fisher's Exact Test is as follows

```
proc freq data = testData_SHP640_PBO;  
tables treatment*CS / chisq nocol nopercent;  
run;
```

Example SAS code for generating exact CI for binominal proportion is as follows:

```
proc freq data = testData_SHP640_PBO;  
tables CS / binomial (exact level='Yes') alpha=0.05;  
by treatment;  
run;
```

Example SAS code for generating the estimated difference in response rates and corresponding 95% asymptotic CI for the difference.

```
proc freq data = testData_SHP640_PBO;  
tables treatment*CS / nocol nopercent cl riskdiff alpha=0.05;  
run;
```

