diff_640_pbo = prop_640 - prop_pbo;  
se_diff_640_pbo = sqrt(prop_640_SE*prop_640_SE + prop_pbo_SE*prop_pbo_SE);  
run;
```

```
*Combine proportion difference estimates;
```

```
proc mianalyze data = trt_diff_640_pb01;  
modeleffects diff_640_pbo;  
stderr se_diff_640_pbo;  
run;
```

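### If outcomes are positively correlated within households, the planned 95% CIs for the SHP640-placebo difference are somewhat too narrow, and the household-adjusted test supplies no interval

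*SAP*

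**What the plan says.** Protocol 6.2.2 and SAP 2.2 let several subjects from one household take part: "Subjects from the same household will be assigned to the same treatment group to which the first enrolled subject in the household was randomized". No cap on household members and no expected share of such subjects is given.

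For the primary endpoint, SAP 10.2 tests with Fisher's exact test and adds an interval: "the estimated difference in response rates and corresponding two-sided 95% asymptotic CI for the difference will also be reported". The example code in SAP 20.2.1 obtains it from the two-by-two table of subjects, "tables treatment*CS / nocol nopercent cl riskdiff alpha=0.05", with no household term. The same kind of interval is planned for:

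- the ITT analysis in SAP 10.3 ("A sensitivity analysis will be conducted by repeating the primary analysis using the ITT Population");
- the modified WOCF analysis in SAP 10.3;
- the CRF-visit analysis in SAP 10.4;
- the key secondary analysis in SAP 10.5, and its version without swabs taken under 12 hours after a dose.

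The multiple-imputation interval combines two independent binomial standard errors: "se_diff_640_pbo = sqrt(prop_640_SE*prop_640_SE + prop_pbo_SE*prop_pbo_SE" (SAP 20.2.2).

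The only analysis that uses households is the adjusted chi-square test in SAP 10.4: "Since all subjects from the same household will be assigned to the same treatment group, an exploratory analysis will be conducted". Its stated output is: "Adjusted Chi-square test statistics and corresponding p value will be presented". SAP 10.5 extends it to the key secondary endpoint ("adjusted Chi-square test and analysis based on CRF visits as exploratory analyses"). Both tables are listed for mITT only in SAP 21. The example code in SAP 20.2.3 computes the within-household correlation (rho) and a variance inflation factor for each arm (C_640 and C_pbo), but prints only the statistic and the p value.

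**The concern.** Within a household, allocation is by cluster. Members share exposure, probably the pathogen, and perhaps dosing habits, so positive correlation is the natural expectation. The true standard error of the difference then exceeds the one used in every planned interval. The SAP corrects a p value for this but leaves uncorrected the interval that readers will use to judge the size of the effect. The ITT interval has no household-aware counterpart at all.

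**Working it through.** **Inputs from the documents.** 216 mITT subjects per arm, 61% vs 45%, ~90% power (Protocol 9.6, SAP 2.5); final two-sided alpha 0.0499 (SAP 2.6); 854 randomized, 366 per arm (Protocol 9.6), or 721 randomized, 309 per arm (SAP 2.5).

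**Assumed, because not in the documents.** Households of two, and the share in pairs and ICC shown in the table.

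**1. The plan's own figure.** Exact enumeration of the two-sided Fisher test at 216 per arm gives power 0.8987, at 0.05 and at 0.0499. The stated ~90% is reproduced for independent subjects.

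**2. The planned interval.** SE = sqrt(0.61×0.39/216 + 0.45×0.55/216) = 0.0474. Half-width = 1.96 × 0.0474 = 9.29 points, so 6.7 to 25.3 around 16. With no clustering its exact coverage is 94.9%.

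**3. Design effect.** The SAP's own factor is C = 1 + (Σm²/M − 1)×rho. With a share s of subjects in pairs, Σm²/M = 1 + s, so DE = 1 + s×ICC. The half-width needed is 9.29×√DE. By normal approximation the planned CI covers 2Φ(1.96/√DE) − 1, which is 94.65%, 94.31%, 93.83% and 92.64% for the four rows. Simulation (400,000 trials per row) gives:

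| mITT share in pairs | ICC | DE | Half-width needed (points) | Planned CI coverage | Household-robust CI coverage |
|---|---|---|---|---|---|
| 10% | 0.3 | 1.03 | 9.4 | 94.6% | 94.9% |
| 20% | 0.3 | 1.06 | 9.6 | 94.2% | 94.9% |
| 20% | 0.5 | 1.10 | 9.7 | 93.7% | 94.9% |
| 40% | 0.5 | 1.20 | 10.2 | 92.6% | 94.9% |

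**4. Which rows are plausible in mITT.** 504/854 = 59% of randomized subjects are expected to stay. If culture positivity is independent within households (an assumption), 20% and 40% of mITT subjects in pairs require 0.20/0.59 = 34% and 0.40/0.59 = 68% of randomized subjects in pairs. That favours the upper rows. Positivity shared within households would weaken this argument.

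**5. ITT.** The same households are not thinned, so the pair share is multiplied by 854/504 = 1.69, or by 721/504 = 1.43. The rates 61% vs 45% are assumed here too.

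| mITT DE | ITT DE (854) | Coverage, 366 per arm | ITT DE (721) | Coverage, 309 per arm |
|---|---|---|---|---|
| 1.03 | 1.05 | 94.3% | 1.04 | 94.4% |
| 1.06 | 1.10 | 93.7% | 1.09 | 93.9% |
| 1.10 | 1.17 | 92.9% | 1.14 | 93.2% |
| 1.20 | 1.34 | 90.8% | 1.29 | 91.5% |

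**6. Key secondary.** The documents give no eradication rates. Over assumed pairs from 40%/25% to 95%/85%, planned coverage is 94.4–94.6%, 94.0–94.2%, 93.5–93.7% and 92.3–92.6% in the same order of DE.

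**7. Fisher's test.** Type I error at 53% in both arms is 3.8% with no clustering, then 4.1%, 4.4%, 4.8% and 5.9%. It is 4.96% at DE 1.12. Power at 61% vs 45% is 89.5%, 89.2%, 88.8% and 87.8%.

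**The case against.** The strongest reply is that the SAP already deals with clustering and that a reader can recover what is missing. The adjusted statistic divides each arm's contribution to the Pearson chi-square by C_640 or C_pbo. With nearly equal arms, Pearson divided by adjusted is therefore close to the design effect. Responder counts are tabulated, and the chi-square option in SAP 20.2.1 outputs Pearson. Scaling the planned SE by the root of that ratio restored coverage to 94.8–94.9% in simulation. This stands for mITT, but the tabulated interval would still under-cover, and ITT has no adjusted statistic to work from.

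Second, the effect is small: 0.3 to 0.7 points of coverage and 0.1 to 0.3 points of half-width at DE 1.03–1.06. That also stands. Third, the code is labelled as an example and table specifications are in a separate document (SAP 1), so rho may yet be reported. The text of SAP 10.4, however, promises only a statistic and a p value.

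A reader might infer more than the documents support:

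- **That the SAP ignores clustering.** It does not. The coded test held 4.9–5.1% type I error in simulation.
- **That Fisher's test is invalid.** Its conservatism absorbs design effects up to about 1.1. It exceeds 4.99% only under heavier clustering, which the documents do not show.
- **That ~90% power is wrong.** It is not materially so at DE 1.03–1.10.
- **That a larger sample after the interim analysis would cure the problem.** It narrows the interval but does not restore coverage: at an assumed 324 or 432 per arm, planned coverage at DE 1.20 is still 92.6–92.7%.

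**Conclusion.** The concern holds as a conditional and modest one. If households contribute several subjects with positively correlated outcomes, the planned intervals for the difference are too narrow by a factor √DE, and no household-adjusted interval is planned. With no multi-member households, or with zero correlation, nothing is lost; with negative correlation the intervals would not be too narrow. The size rests wholly on assumed household structures. In mITT, coverage falls to between 94.6% and 92.6% over DE 1.03–1.20, with the upper part of that range likelier. For the same households in ITT it falls to between 94.3% and 90.8% at 854 randomized. The confirmatory conclusion is unaffected, so this is an improvement worth making and not a flaw that endangers the trial.

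**What to change.** Before unmasking, keep Fisher as the sole confirmatory test, leave the point estimate unchanged, and amend the SAP:

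1. In 10.2, 10.5 and the ITT table of 10.3, report a household-adjusted 95% CI for the difference beside the planned one. Use either SE² = C_640×p1×q1/M_640 + C_pbo×p2×q2/M_pbo, from quantities already in 20.2.3, or a cluster-robust variance on HOUSEID with working independence.
2. Apply the same variance within each imputation for multiple imputation, and to the modified WOCF, CRF-visit and under-12-hour-swab intervals. Otherwise label those as assuming independence.
3. Print rho and the number and share of subjects in multi-member households.
4. State that Fisher alone determines significance when it and either CI disagree, in either direction.

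The cost is SAP text and one extra interval per table. Fisher is unchanged and Protocol 9.8.2 leaves the detailed plan to the SAP, so no protocol amendment is needed. The adjusted CI is about 1.5% to 9.5% wider (√1.03 − 1 to √1.20 − 1).

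Showing both intervals also creates some disagreement to explain. At 61% vs 45%, Fisher differs from at least one CI on significance in about 1.6–1.7% of trials at DE 1.03–1.10, as with the planned CI alone, and in about 3.1% at DE 1.20. The two CIs differ on whether zero is included in about 0.1%, 0.6%, 1.4% and 3.1% of trials at the four design effects.

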Appendix 20.2.3 shows example SAS code for the adjusted chi-square test.

Analysis Based on CRF Visits

Analysis visits in the primary analysis will be derived based on rules specified in Section 18.2 of this SAP. An exploratory analysis will be conducted repeating the primary analysis on the primary efficacy endpoint of clinical resolution in the study eye at Visit 3 (Day 5) in mITT based on CRF recorded Visit 3 data. Frequency and percent of subjects who reached/did not reach clinical resolution in the study eye at Visit 3 will be reported by treatment group along with the two-sided Fisher's Exact test p value for comparison between SHP640 and placebo. The two-sided 95% CI for response rate (exact CI for binominal proportion) in each treatment group as well as the estimated difference in response rates and corresponding two-sided 95% asymptotic CI for the difference will also be reported.

10.5 Key Secondary Efficacy Endpoints and Analysis

The key secondary efficacy endpoint of this study is bacterial eradication status (defined as absence of all bacterial species present at or above pathological threshold at baseline) in the study eye at Visit 3 (Day 5) between SHP640 and placebo.

The null hypothesis to be tested is that there is no difference in proportion of subjects reaching bacterial eradication in the study eye at Visit 3 (Day 5) between SHP640 and placebo with the alternative hypothesis of non-zero difference in the proportion of responders between the two treatment groups.

In order to maintain the study-wide Type I error at 5% (two sided alpha of 0.0001 at IA and two sided alpha of 0.0499 at final analyses), the primary and key secondary hypotheses will be tested sequentially using two-sided Fisher's exact test with the primary efficacy endpoint being tested first and the key secondary efficacy endpoint being tested second. The hypothesis test for the key secondary efficacy endpoint will not be performed unless the hypothesis test for the primary efficacy endpoint is statistically significant.

Missing data will be imputed based on the post baseline LOCF for the determination of bacterial eradication status in the study eye at Visit 3 (Day 5). The primary basis of inference for the key secondary comparison will be based on the analysis conducted in mITT. Frequency and percent

of responders in the study eye at Visit 3 (Day 5) will be reported by treatment group along with the two-sided Fisher's Exact test p value for comparison between the two treatment groups. The two-sided 95% CI for response rate (exact CI for binominal proportion) in each treatment group as well as the estimated difference in response rates and corresponding two-sided 95% asymptotic CI for the difference will also be reported.

Sensitivity and exploratory analyses will also be conducted on key secondary efficacy endpoint using the same methods as described in Section 10.3 and 10.4 (i.e. modified WOCF imputation and multiple imputation as sensitivity analyses; adjusted Chi-square test and analysis based on CRF visits as exploratory analyses) except for the ITT population sensitivity analysis, which will not be conducted for bacterial eradication key secondary endpoint.

In addition, a subgroup analysis will be conducted by repeating the Fisher's exact test with post baseline LOCF for the determination of bacterial eradication status in the study eye at Visit 3 (Day 5) in the mITT excluding bacterial eradication data obtained from swabs where the last dose of study medication was instilled within 12 hours of the swab (i.e. swab occurred <12 hours after last dose of investigational product). Frequency and percent of responders in the study eye at Visit 3 (Day 5) will be reported by treatment group along with the two-sided Fisher's Exact test p value for comparison between the two treatment groups. The two-sided 95% CI for response rate (exact CI for binominal proportion) in each treatment group as well as the estimated difference in response rates and corresponding two-sided 95% asymptotic CI for the difference will also be reported. This subgroup analysis is not statistically powered.

10.6 Other Secondary Efficacy Endpoints and Analysis

Secondary efficacy endpoints are defined as follows:

- Clinical resolution status of bacterial conjunctivitis at Visits 2 (Day 3), 4 (Day 8), and 5 (Day 12) in the study eye
- Bacterial eradication status (defined as absence of all bacterial species present at or above pathological threshold at baseline) as assessed by bacterial culture at Visits 2 (Day 3), 4 (Day 8), and 5 (Day 12) in the study eye
- Absolute and change from baseline of the individual clinical signs score (bulbar conjunctival injection and ocular conjunctival discharge) at Visits 2 (Day 3), 3 (Day 5), 4 (Day 8), and 5 (Day 12) in the study eye
- The global clinical score (defined as the sum of bulbar conjunctival injection and ocular conjunctival discharge) and change from baseline in the global clinical score at Visits 2 (Day 3), 3 (Day 5), 4 (Day 8), and 5 (Day 12) in the study eye
- Modified clinical resolution status, defined as a global clinical score of 0 or 1, at Visits 2 (Day 3), 3 (Day 5), 4 (Day 8), and 5 (Day 12) in the study eye
- Expanded clinical resolution status, defined as a global clinical score of 0, 1, or 2 with neither injection nor discharge having a score of 2, at Visits 2 (Day 3), 3 (Day 5), 4 (Day 8), and 5 (Day 12) in the study eye

- Time to clinical resolution based upon assessments at Visits 2 (Day 3), 3 (Day 5), 4 (Day 8), and 5 (Day 12) in the study eye
- Use of rescue medication

All secondary efficacy analyses will be performed on the mITT and presented by treatment group. No hypothesis testing will be conducted for the secondary efficacy endpoints. All secondary efficacy endpoints will be summarized by treatment group using descriptive statistics at each assessment visit. Continuous endpoints will be summarized by number of subjects (n), mean, median, SD, minimum, maximum and two-sided 95% CI. Binary endpoints will be summarized by number of subjects (n), frequency, proportion and two-sided 95% CI (exact CI for binominal proportion). Time to event endpoint will be summarized by Kaplan-Meier survival estimates (number of events, number at risk, survival function at each assessment visit, median survival time and 95% CI). Survival plot by treatment group will also be generated.

